6.1 Study Visit Summaries

6.2 Screening:

The subject will provide written informed consent prior to screening. The study will be explained to each subject. An Informed Consent Form (ICF) will be signed by each subject before study participation as mandated by FDA regulations and the institutional review board (IRB). (See Appendix B) A blank copy of the IRB approved informed consent form must be kept on-site and by Tactile Medical™. A copy of the ICF will be given to the subject to read and take home to consider, if they prefer. All the subject's questions must be answered prior to signing the ICF. Research procedures cannot be performed until the subject provides consent. The signed original for each subject must be kept in the subject's research records. A copy of the signed consent form will be given to each subject.

After informed consent is obtained, screening will commence. (See Appendix C: Screening Form) The subject's head and neck measurements will be taken to assist with garment size selection. For subjects with a tracheostomy, the fit will be accessed further to ensure that the garments do not interfere with their tracheostomy. The head and neck garment measuring guide is included in Appendix A. Should the head and neck measurements indicate the garment will not fit, no further information will be obtained and the subject will be withdrawn. After the garment fit has been confirmed the remaining inclusion and exclusion criteria will be evaluated to ensure that the subject meets all entrance criteria. The subject should not undergo any study specific procedures until after the informed consent process and screening processes are complete.

6.3 Baseline Visit:

The screening and baseline visit can occur on the same day or different days depending on the needs of the subject. At this visit, the subject will undergo the baseline data collection procedures as outlined in the Study Schedule of Activities in section 7.4.

Randomization:

After completing the informed consent process and baseline data collection (including the endoscopy) subjects enrolled at each site will be randomized (1:1) to either the investigational group or wait-list control group via the use of a computer-generated, permuted block program executed by the study biostatistician. Each site will have its own unique randomization list.

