Aim 2 (preliminary efficacy): Descriptive and graphical summaries of the measures at each time of assessment will summarize the overall and group changes in each of the outcome measures over the 8-week study period for each of the groups. Mixed effects general linear models will be used to generate estimates of the interactive effect of the Flexitouch® Head and Neck Garment and time in the study on the primary outcomes. Such an interaction effect would be indicate, for example, larger reduction in symptoms for the intervention group than that observed in the wait list control over the same time period. Bias-corrected effect sizes of garment use on the respective changes will be generated from each of the outcomes. While this study is a preliminary study of efficacy and effect sizes, a maximum alpha level of .05 will be used for statements of “statistical” significance.

Safety Analysis: During the time any participant is using the device, safety checks (Adverse Evetns-CTCAEV4.0, B/P, Pulse, and staging) will be made at defined intervals as noted in section 7.3.

Determination of Sample Size: The primary rationale for study size is the proposed funded time of this study and the number of potential subjects that could be recruited during that time. This is not a hypothesis testing study rather it is a preliminary feasibility and efficacy study for generating observed effect sizes. Nevertheless, samples of 20 individuals in each group (total=40) who successfully complete the 8-week protocol will provide 80% statistical power to detect a differential level of change of approximately 0.9SD (effect size). In other words, assuming a baseline Neck Disability Index (NDI) of 20 (SD=10) and that the wait-list control group demonstrates no change from baseline, a reduction in mean NDI to 11 in the garment group would indicate a statistically significant difference (2-sided alpha-0.05). We have no evidence to hypothesize differences of that magnitude however; we do believe that our sample size will provide sufficient data for estimating reasonable effect estimates for future studies.

13.0 Compensation:

Subjects may be compensated for time and travel at an amount determined by each site.

14.0 Publication Plan:

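### Section 12.4 disclaims hypothesis testing but permits unadjusted significance statements at .05 across some 15 to 37 efficacy outcomes, with no lead outcome and no confidence intervals

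*Combined protocol and SAP*

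**What the plan says.** Two statements in section 12.4 pull in different directions. Under Determination of Sample Size the plan states: "This is not a hypothesis testing study rather it is a preliminary feasibility and efficacy study for generating observed effect sizes". Under Aim 2 it says that "a maximum alpha level of .05 will be used for statements of" statistical significance. That sentence opens by acknowledging that the study is preliminary, and the plan puts the word statistical in quotation marks.

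On the scope of the analyses, Aim 2 says: "Bias-corrected effect sizes of garment use on the respective changes will be generated from each of the outcomes". The mixed models, by contrast, are tied to the primary outcomes. Section 5.2.1 lists the primary endpoints as adherence and its barriers, adverse events and satisfaction, so that term has no defined meaning for efficacy. The example given with the models, a larger reduction in symptoms, suggests that efficacy outcomes are meant.

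Sections 12.3 and 12.4 name no single lead efficacy outcome, give no multiplicity rule and mention no confidence interval for Aim 2. Section 7.2.6.1 describes the Vanderbilt Head and Neck Symptom Survey (VHNSS) as having 13 domains, and section 7.2.7 describes a 5-item quality-of-life scale. Neither says whether a total or the separate parts will be analysed.

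**The concern.** A trial meant to supply effect sizes for later studies gains little from a significance threshold. If the threshold is applied across many outcomes, some may cross it by chance and be reported as efficacy findings. With the number of outcomes unsettled, how many are tested could be decided after the data are seen.

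The threshold also works against the stated purpose. At 20 per arm an outcome must show an observed difference of roughly 0.64 SD to reach p<.05, so the outcomes singled out as significant are those whose estimates are most likely to be too large. Without intervals, a reader planning the next study cannot see how imprecise any estimate is. Section 12.3 says blinding is not possible and several outcomes are self-reported, so a significance label is easily over-read. That source of bias is separate from the chance error calculated here.

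**Working it through.** **1. The plan's own figure.** Section 12.4 counts on 20 completers per arm, 40 in all, and claims that this number "will provide 80% statistical power to detect a differential level of change of approximately 0.9SD (effect size"). The illustration is "assuming a baseline Neck Disability Index (NDI) of 20 (SD=10") with a fall to 11 in the device group, so the difference is (20 − 11)/10 = 0.9 SD. Section 6.3 gives 1:1 allocation.
- Normal approximation: 0.9 × √(20/2) = 2.846; power = Φ(2.846 − 1.960) = 81.2%.
- Noncentral t with 38 degrees of freedom: 79.2%.

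The stated 80% is reproduced.

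**2. Number of efficacy outcomes.**

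| Measure (section) | By instrument | By domain and item |
|---|---|---|
| Firm inflammatory markers (7.2.4.2) | 5 | 5 |
| Modified Patterson Scale (7.2.4.1) | 1 | 1 |
| External lymphedema grade (7.2.4.4) | 1 | 1 |
| Neck Disability Index, NDI (7.2.5.1) | 1 | 1 |
| Voice Handicap Index (7.2.5.2) | 1 | 1 |
| Range of motion: cervical, shoulder, jaw (7.2.5.3, 7.2.5.4) | 3 | 3 |
| VHNSS (7.2.6.1) | 1 | 13 |
| Lymphedema symptom survey (7.2.6.2) | 1 | 1 |
| Quality of life (7.2.7) | 1 | 5 |
| **Total** | **15** | **31** |

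Adding photographs (1), the General Symptom Survey as one score (1), the trismus grade (1) and the three markers that depend on test availability (3) gives 31 + 6 = 37.

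**3. Chance findings with no true effect, independent outcomes.** The plan's illustration is explicitly two-sided: "a reduction in mean NDI to 11 in the garment group would indicate a statistically significant difference (2-sided alpha-0.05"). Each test therefore has a 5% chance of p<.05 in either direction and a 2.5% chance in favour of the device.
- Either direction: 1 − 0.95^31 = 79.6%; 1 − 0.95^15 = 53.7%.
- Benefit only: 1 − 0.975^31 = 54.4%; 1 − 0.975^15 = 31.6%.
- Expected number among 31: 31 × 0.05 = 1.55 in either direction; 31 × 0.025 = 0.78 in favour of the device.

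**4. Correlated outcomes.** All outcomes come from the same patients, and the documents give no correlations. I assume one common correlation ρ between normally distributed test statistics and integrate numerically over the shared component.

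| ρ (assumed) | 31, either direction | 31, benefit | 15, either direction | 15, benefit |
|---|---|---|---|---|
| 0 | 80% | 54% | 54% | 32% |
| 0.3 | 67% | 36% | 46% | 23% |
| 0.5 | 51% | 26% | 36% | 18% |

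A four-domain structure for 31 outcomes, with assumed correlations of 0.3 within and 0.1 between domains, gives 73% in either direction and 43% for benefit. With 0.5 and 0.2 it gives 64% and 35%.

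**5. Precision.** The 95% half-width for a difference between two groups of 20, in SD units, is t(0.975; 38) × √(1/20 + 1/20) = 2.024 × √(2/20) = 0.64. This is a simple two-group approximation; the mixed model may give a somewhat different width.

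**The case against.** The plan is candid about its limits. Efficacy is a secondary aim and is called preliminary; .05 is set as a maximum; and the sample-size paragraph says there is no evidence to expect a difference of 0.9 SD. Pilot studies commonly forgo multiplicity control. Bonferroni over 31 tests (0.05/31 = 0.0016) would cut power at 0.9 SD to about 38%. All of this stands. It makes the problem smaller, and it rules out multiplicity adjustment as the sensible remedy. It does not give the significance sentence a purpose: if the study is exploratory, the label adds nothing that an estimate and its interval would not show better.

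Four stronger readings might be inferred, and the documents do not support them.
- **A chance significant benefit is more likely than not.** With two-sided tests only the results in the device's favour count. The probability passes 50% only with at least 28 independent tests (1 − 0.975^28 = 50.8%; 27 give 49.5%). For 31 tests it falls below 50% once a common correlation exceeds about 0.06.
- **There are at least 31 tests.** That count requires separate analysis of 13 domains and 5 items, which the plan does not state. By instrument it is 15.
- **The plan commits to a test of every outcome.** Effect sizes are planned for each outcome, but the models refer to the undefined primary outcomes. The significance sentence sets no limit on which results it covers; it also lists no tests.
- **The NDI is the natural lead outcome because the study was sized on it.** Section 12.4 bases the size mainly on funded time and recruitable subjects and uses the NDI only to illustrate 0.9 SD. The secondary aim in section 4.4 does not name the NDI.

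**Conclusion.** The concern holds in a limited form. Section 12.4 states an estimation purpose and then permits unadjusted significance statements over a large, unsettled set of efficacy outcomes, with no lead outcome and no intervals. If nothing is truly different and the rule is applied across the set, at least one significant difference in some direction has a probability of 80% to 51% for 31 outcomes and 54% to 36% for 15. At least one false benefit has a probability of 54% to 26% and 32% to 18%, where a single test would carry 2.5%. These ranges rest on the outcome counts above, on assumed correlations of 0 to 0.5, and on every counted outcome being tested once. The matter is worth correcting before analysis because it changes what the report may claim; it does not touch the feasibility aim.

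**What to change.** In section 12.4, Aim 2, replace the significance sentence with text along these lines: every Aim 2 effect size will be reported with its 95% confidence interval; any p-values are nominal and unadjusted for multiple outcomes; no conclusion about efficacy will rest on them. No multiplicity adjustment is needed.

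The same edit should say which outcomes the mixed models cover, since primary outcomes is undefined for Aim 2, and whether the VHNSS and the quality-of-life scale are analysed as totals or by domain and item.

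The cost is SAP wording only, with no change to sample size, visits or data collection. The sponsor gives up significance labels on individual outcomes, and the wide intervals will show openly how little a trial of this size can settle about efficacy.
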